Pilot Study: Comparing the Effects of Hydroxychloroquine (HCQ) to Pioglitazone in Type 2 Diabetic Patients Failing Maximal Doses of Metformin Plus a Sulfonylurea

ClinicalTrials.gov NCT02303405

Protocol

Last Modified: January 11, 2017

Pilot Study: Comparing the Effects of Hydroxychloroquine (HCQ) to Pioglitazone in Type 2 Diabetic Patients Failing Maximal Doses of Metformin Plus a Sulfonylurea

Background: Type 2 diabetes is characterized by insulin resistance (decreased insulin sensitivity), as well as an increased inflammatory state. It is unclear whether insulin resistance causes the inflammatory state, whether the inflammatory causes the insulin resistance, or whether each is independent of the other (Shoelson SE et al, J Clin Invest 2006; 116:1793-1801). The LA County DHS formulary for treating type 2 diabetes is currently limited to metformin, two sulfonylurea agents (SU), pioglitazone (a thiazolidinedione, or TZD) and insulin. The treatment algorithms utilized in the Diabetes Programs at the Martin Luther King Jr. Outpatient Center (MLK) and the South Central Family Health Center (SCFHC) start with metformin, after which an SU is added, and if maximum doses of both do not control patients, a maximum dose of pioglitazone is then added. We have previously published our experience with TZDs (both rosiglitazone and pioglitazone) as the third drug and found that TZDs lower HbA_{1c} levels approximately 2.0% (from a baseline value of 9.3-9.5%) with two-thirds of our patients meeting our target of <7.5% after 4 months, which avoids starting insulin at that time (Tran MT, et al. Diabetes Care 2006; 29:1395-1396). As long as HbA_{1c} levels can be maintained <7.5%, insulin is not necessary according to the treatment algorithms in the Diabetes Program at MLK-MACC. Unfortunately, although they reduce insulin resistance, TZDs may be prone to side effects including fluid retention, heart failure, weight gain, and decreased bone mineral density leading to increased fracture risk in susceptible individuals.

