Secondary Outcomes: To collect preliminary data to eventually compare a) the percentage of patients who achieve HbA_{1c} <7.5% after receiving either HCQ or PIO for 4 months; b) the effect of PIO vs. HCQ in lowering fasting plasma glucose (FPG) and weight; and c) the effects of HCQ vs. PIO on inflammation and insulin resistance.

Research Design: A 4-month, randomized, prospective, open-label comparison trial

Subjects: Type 2 diabetic patients inadequately controlled on maximally tolerated doses of metformin plus a SU.

Recruitment: Subjects will be recruited from the Diabetes Programs at MLK and South Central Family Health Center (SCFHC). These centers serve the same large population of low-socioeconomic status and low-educational level ethnic minority patients living in the south and south-central region of Los Angeles. The diabetes clinic at MLK is staffed by the faculty of the Endocrinology Division of Charles R. Drew University of Medicine and Science, and the diabetes care providers at the SCFHC clinic were trained on the same treatment protocols by the study co-investigator. This study protocol will be reviewed by the Institutional Review Board of Charles R. Drew University prior to study initiation, and an IND application will be submitted to the FDA.

Inclusion Criteria:

- Male or female, age 18-75, inclusive
- Known type 2 diabetes (diagnosed according to 1997 ADA diagnostic criteria) receiving diabetes treatment at MLK or SCFHC
- At least 3 months of treatment with maximum tolerated doses of metformin *and* a SU, *and* inadequate glycemic control (HbA_{1c} ≥ 7.5% and < 11.0%)
- Body mass index (BMI) < 45 kg/m²
- Able to comply with all scheduled visits and requirements of the protocol

Exclusion Criteria:

- Any contraindications to the use of metformin or a SU
- Extreme hyperglycemia (FPG ≥ 300 mg/dL), symptoms of polyuria or polydipsia, or HbA_{1c} ≥ 11.0%
- Current use of insulin; history or clinical suspicion of type 1 diabetes mellitus
- Symptomatic hypoglycemia occurring at an average frequency > once per day
- Highly erratic dietary schedules, extremely food insecure households, or homelessness that may adversely affect good glycemic control, as judged by the investigators
- Occupations that involve regular operation of motor vehicles or other heavy machinery that may pose a hazard in the event of unanticipated blurred vision

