- Known history of Class III or IV heart failure, cardiac arrhythmias, severe peripheral edema, advanced osteoporosis, documented bladder malignancies, or other intolerance to PIO
- Known history of collagen vascular disorders, glucose-6-phosphate dehydrogenase deficiency, hematologic disorders, psoriasis, or any known intolerance to HCQ

- Known history of pre-proliferative or proliferative retinopathy, or any clinically significant retinal abnormalities noted on the patient's most recent (i.e., within 1 year) ophthalmologic exam; subjects who have not received their routine annual ophthalmologic surveillance for diabetic retinopathy within the past year must have their annual surveillance performed before screening
- An estimated GFR (by the Modification of Diet in Renal Disease (MDRD) formula) < 45 mL/min, or a history of nephrotic syndrome (defined as a spot urine protein-creatinine ratio of > 3500 mg per g urine creatinine)
- Subjects with active hemoglobin abnormalities that render the HbA_{1c} measurement unreliable
- History of any clinically significant hepatic, cardiovascular, infectious, dermatologic, psychiatric, or other major systemic disease that, in the opinion of the investigator, may make the use of PIO or HCQ unsafe, or otherwise make the interpretation of the data difficult.
- Female subjects of childbearing potential who are sexually active and not using a reliable form of contraception or do not agree to use a reliable form of contraception. Reliable forms of contraception include systemic contraceptives (oral, implant or injection), diaphragm with spermicide, cervical cap, IUD, or condoms with spermicide.
- Current pregnancy or lactation.
- Subjects who will likely require or initiate therapy with drugs that may interfere with glucose metabolism during the course of the study (e.g., glucocorticoids).
- Subjects who are in another investigational study or have received another investigational medication within 30 days of study entry
- Subjects who are unable or unwilling to give informed consent, comply with all components of the study protocol, attend all scheduled follow-up visits, or present other barriers that would make the implementation of the protocol unusually difficult.

Schedule of Procedures: This study will be approximately 4 months in duration. Subjects will be assessed at baseline, 2 and 4 months. All visits will include an assessment of:

- Fasting plasma glucose (FPG)
- HbA_{1c}

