- Compliance with the study medication will be verified with pill counts at each follow-up visit. The need for consistent use of the study medication will be reinforced if suboptimal compliance is noted.
- Adverse events and any clinically meaningful changes in physical findings will be noted. The probability of any causal relationship between the adverse event or physical finding

and the study intervention will be judged by the investigator and if necessary, reported to the IRB.

- Hypoglycemic episodes, as defined by the presence of appropriate symptoms that are alleviated by the ingestion of carbohydrates or associated with a confirmed FPG level < 60 mg/dL, will be assessed. If necessary, subjects will be instructed on how to manage hypoglycemic reactions if they have not previously received such instructions. The frequency and timing of episodes will be noted. Possible precipitants of hypoglycemia will be reviewed and corrective measures will be advised if correctable precipitants are identified. If necessary, the subject's SU dosage may be down-titrated to alleviate any recurrent hypoglycemic episodes.

Withdrawals: Subjects may either voluntarily withdraw from the study or be withdrawn by the investigators. A subject who withdraws from the study for any reason will continue to be followed for their diabetes in their respective Diabetes Clinic after their study participation is terminated. Reasons for study withdrawal by the research team include, but are not limited to, excessive non-compliance with the study medication, repeated failure to attend scheduled visits, use of any other medications known to affect glucose or lipid control, adverse effects (including confirmed FPG ≥ 300 mg/dL or clinically significant hypoglycemia not relieved by nutritional modifications or downward titration of the SU) or any other clinical situation which, in the opinion of the investigators, may jeopardize the subject's safety.

Methodologies:

Anthropometric Measurements: Standard procedures will be followed for the measurement of vital signs, weight, height, and calculated BMI.

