Laboratory Measurements: All laboratory analyses except fasting insulin and hsCRP will be obtained by the respective clinic phlebotomists specified above, and conducted by the respective clinical laboratories specified above, or the CTRC. Samples for insulin and hsCRP levels will be obtained at the CTRC, banked, and will be measured in the future by the CTRC Core Lab using commercially available RIA and/or ELISA kits: Millipore HI-14K Human Insulin RIA (Millipore, Billerica, MA); MP Biomedicals 07BC-1119 ultrasensitive CRP ELISA (MP Biochemicals, Orangeburg, NY); samples for insulin and hsCRP will remain frozen until assay reagents are available for batched runs once all samples have been collected.

Statistical Analyses:

All data will be collected onto Excel spreadsheets. Non-normal data will be log-transformed, as appropriate.

Intended Primary Endpoint: *The between-group change in the HbA_{1c} level from baseline to 4 months.*

Intended Secondary Endpoints:

A) The between-group difference in the change by 4 months of: i) % of subjects achieving HbA_{1c} $< 7.5\%$, ii) FPG, iii) weight and BMI, iv) HOMA-IR and QUICKI, and v) hsCRP and leukocyte counts;

B) For each group, the within-group change by 4 months in HbA_{1c}, FPG, weight and BMI, HOMA-IR and QUICKI, hsCRP, and leukocyte counts;

C) The between-group difference in the incidence of i) all hypoglycemic events, ii) severe hypoglycemic events, and iii) all adverse events excluding hypoglycemia.

Analysis: Changes in all continuous outcome measures will be compared between groups using 2-way repeated measures ANOVA. A chi-square analysis will be used to compare the percent of subjects achieving HbA_{1c} $< 7.5\%$ between groups. Changes within groups between baseline and

4-months will be made with one-way ANOVA. We will plan to eventually conduct both an intent-to-treat (ITT) analysis (missing data imputed using last-observation carried forward) as well as a secondary analysis of only those completed subjects with mean medication compliance $\geq 90\%$.

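### For the secondary HbA1c <7.5% endpoint, the general LOCF rule can count a week-8 value as a 4-month success, and neither planned analysis counts that early leaver as a failure

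*Combined protocol and SAP*

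**What the plan says.** All references are to the combined protocol and SAP.

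- Secondary Outcomes, item (a), concerns the percentage with HbA1c "<7.5% after receiving either HCQ or PIO for 4 months".
- Background explains why the 7.5% target matters: reaching it on a third drug is something "which avoids starting insulin at that time".
- Statistical Analyses, Intended Secondary Endpoints A, lists "The between-group difference in the change by 4 months of: i) % of subjects achieving" the target, alongside the continuous endpoints.
- The Analysis paragraph names the test, "A chi-square analysis will be used to compare the percent of subjects achieving" the target, and then two analyses. One is an "intent-to-treat (ITT) analysis (missing data imputed using last-observation carried forward"). The other is described as "as well as a secondary analysis of only those completed subjects with mean medication compliance" of at least 90%. No separate missing-data rule is given for the responder endpoint.
- Schedule of Procedures: "Subjects will be assessed at baseline, 2 and 4 months". The only post-baseline HbA1c values are therefore at weeks 8 and 16.
- Inclusion Criteria require an entry HbA1c of at least 7.5% and below 11.0%.
- Withdrawals lists reasons for removal by the research team, among them "use of any other medications known to affect glucose or lipid control, adverse effects" (including a confirmed FPG of 300 mg/dL or more), non-compliance and missed visits. After withdrawal the subject returns to clinic care. No week-16 study HbA1c is required.

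**The concern.** Withdrawal after week 8 will usually leave the week-16 HbA1c missing, and the LOCF rule then puts the week-8 value in its place. A subject at 7.2% at week 8 who is later withdrawn for an adverse effect, or for a confirmed FPG of 300 mg/dL or more, would be reported as having met the 4-month target. A subject withdrawn for the same adverse effect before week 8 would be reported as having missed it. That sits badly with an aim worded around 4 months of treatment.

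The responder rate speaks directly to the practical question in the Background: how often a third drug keeps patients below 7.5%. Sample Size Calculations says that the pilot's data will inform whether to seek funding for full enrolment. The descriptive rates therefore matter even though the pilot is not powered for the comparison.

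**Working it through.** **Step 1. Classification under each rule.** The baseline value is taken to be the qualifying one.

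| Subject | ITT with LOCF | Completers, compliance ≥90% | Missing week 16 = not achieving |
|---|---|---|---|
| Leaves before week 8 | Failure (entry value ≥7.5%) | Excluded | Failure |
| Leaves after week 8, week-8 value ≥7.5%, no week-16 value | Failure | Excluded | Failure |
| Leaves after week 8, week-8 value <7.5%, no week-16 value | **Success** | Excluded | Failure |
| Stops drug but has a week-16 value | Observed value | Depends on completion and compliance | Observed value |

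Only the third row differs between the first and last rules. Leavers before week 8 add nothing to the gap.

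**Step 2. Inputs.** The plan states no figure for this endpoint, so there is none to reproduce.

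- p, response among those with a week-16 value: 2/3, the historical thiazolidinedione rate in the Background.
- d, share lost after week 8 with no week-16 value: 5% to 30%, assumed. The documents give no withdrawal rate.
- q, share of those with week-8 HbA1c <7.5%: 0.20 to 2/3, assumed. The top value supposes that week-8 response already equals the 4-month rate.
- n: 30 per arm, assumed. The protocol gives only a funding limit of 60 in total.

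**Step 3. Rate per arm.** All loss is placed after week 8.

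- LOCF: (1 − d)p + dq
- Missing as failure: (1 − d)p
- Gap: dq

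| d | Missing as failure | LOCF | Gap (points) |
|---|---|---|---|
| 5% | 63.3% | 64.3–66.7% | 1.0–3.3 |
| 10% | 60.0% | 62.0–66.7% | 2.0–6.7 |
| 20% | 53.3% | 57.3–66.7% | 4.0–13.3 |
| 30% | 46.7% | 52.7–66.7% | 6.0–20.0 |

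Example: at d = 20% and q = 0.40, LOCF gives 0.80 × 0.667 + 0.20 × 0.40 = 61.3%, against 0.80 × 0.667 = 53.3%. The gap is 8.0 points, or 2.4 of 30 subjects. One reclassified subject moves an arm by 1/30 = 3.3 points.

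**Step 4. Difference between arms.** The two rules differ by d_H·q_H − d_P·q_P (H for HCQ, P for PIO), which is zero when late loss and q are equal in both arms. Take 5% late loss on HCQ, 20% on PIO, and p = 2/3 in both:

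- Missing as failure: 63.3 − 53.3 = 10.0 points.
- LOCF: 64.3 − 57.3 = 7.0 at q = 0.20; 65.3 − 61.3 = 4.0 at q = 0.40; 66.7 − 66.7 = 0 at q = 2/3.
- The rules therefore differ by 0.15q, that is 3, 6 or 10 points.

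If the loss rates are swapped between arms, every sign reverses.

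**Step 5. Scale.** With rates of 0.50 and 0.667 and 30 per arm, the SE of the difference is √(0.25/30 + 0.222/30) = 0.125, or 12.5 points. The 3 to 10 point shift is about 0.2 to 0.8 of one SE.

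**The case against.** **The wording conflict is soft.** The Secondary Outcomes entry is a statement of aims, and its reference to 4 months of treatment can be read as a time label. A reader might infer that the protocol sets an on-drug condition which the analysis then breaks, but the text does not go that far. This stands. What remains is that the plan has no dropout rule for this endpoint other than a general one that fits it poorly. Even that is an inference from general wording, since LOCF is not stated for this endpoint by name.

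**Not everyone who stops after week 8 becomes a success.** A reader might infer that they do. In fact it takes both a week-8 value below 7.5% and a missing week-16 value. A subject who stops the drug but attends week 16 is scored on the observed value, and LOCF plays no part. This stands too.

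**A completer analysis is planned.** It is close to the wording of the aim. But it is secondary, and it removes early leavers from the denominator. A week-8 responder who then leaves is a success in one analysis and absent from the other.

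**Inflation depends on the comparator.** LOCF is above the missing-as-failure rate but at or below the completer rate (66.7% in the table). LOCF thus dilutes the effect of leaving on the rate and does not wholly hide it. Adverse events are also compared separately under endpoint C. This is fair, and it limits the claim to the count of subjects who reached the target at 4 months.

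**Counting missing values as failures has its own cost.** With equal response among completers, it yields a 10-point difference in the example purely from unequal leaving, and missed visits need not reflect the drug. This stands as the downside of the fix.

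**Conclusion.** The point holds in a limited form. Read literally, the plan lets a week-8 HbA1c below 7.5% stand as a 4-month success for a withdrawn subject, whatever the reason for withdrawal. Neither planned analysis reports how many randomized subjects reached the target at 4 months. The effect per arm is 2 to 7 points at an assumed 10% late loss and 4 to 13 at an assumed 20%. The arm difference moves mainly when late loss differs between arms. In the 5% versus 20% example it is 0 to 7 points under LOCF and 10 with leavers as failures, a shift below one SE.

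Every loss rate, the week-8 response among leavers and the 30 per arm are assumptions. The direction cannot be predicted, because the documents do not say which arm will lose more subjects late. A reader might also infer that subjects who stopped the drug or added another glucose-lowering drug should be failures even with an observed week-16 value. The documents do not settle that. It is a separate choice of estimand and this point does not depend on it. The endpoint is secondary in a pilot that states it cannot reach its intended power, so this is a worthwhile clarification and not a threat to the trial's main result.

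**What to change.** Change Intended Secondary Endpoints A(i) and the Analysis paragraph as follows:

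- For A(i), replace *by 4 months* with *at the Week 16 visit*.
- Use all randomized subjects as the denominator.
- Count a subject with no Week 16 HbA1c as not achieving the target.
- Keep the LOCF version and the completer set (compliance at least 90%) as named sensitivity analyses.
- Align the wording of Secondary Outcomes (a) with this definition.

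The cost is a few sentences, with no new visits, samples or data. Responder rates will be somewhat lower, and loss to follow-up unrelated to the drug will also count as failure. Reporting the number with a missing Week 16 value by arm, with reasons, would let readers judge how much that matters.

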Screening Visit (Week 0): Consent, screening, review of inclusion and exclusion criteria, and all required subject assessments for the study will take place at the CDU CTRC. A signed authorization for the release of medical records from MLK or SCFHC for the purposes of this study will be needed from all consented subjects to permit the investigators to review the relevant results when they become available. If all entry criteria are met, blood will be taken for the following laboratory tests: CBC, electrolytes, BUN, creatinine, FPG, HbA_{1c}, AST, ALT, fasting insulin, and hsCRP; urine will be collected for a urine pregnancy test (for women of childbearing potential). For subjects from MLK, all blood and urine samples with the exception of fasting insulin and hsCRP will be drawn by the MLK outpatient phlebotomists as per the diabetes clinic's routine treatment protocols, and the investigators will retrieve those results for review when they become available; fasting insulin and hsCRP blood samples will be obtained separately by phlebotomists at the CTRC. The above laboratory tests with the exception of fasting insulin and hsCRP are not required if they have already been performed by the laboratory within the previous 4 weeks and the results are accessible to the study team. For subjects from SCFHC, any of the above laboratory test results performed within the previous 4 weeks will be requested by the investigators, and any that were not performed within the previous 4 weeks will be drawn by the CTRC (including the fasting insulin and hsCRP).

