as with Week 0, all samples except fasting insulin and hsCRP will be obtained by the MLK phlebotomists and results will be reviewed when available; urine will be collected and processed by the MLK laboratory for a urine pregnancy test for women of childbearing potential at each follow-up visit; fasting insulin and hsCRP samples will be obtained separately at the CTRC. For subjects from SCFHC, all samples will be obtained at the CTRC (since the distance from SCFHC to CDU makes obtaining routine lab tests at SCFHC unrealistic when visits must take place at the CTRC). Based on current clinical evidence, diabetic patients are not required to perform self-glucose monitoring in the absence of insulin use, although subjects may perform self-glucose monitoring on their own if desired. Any hypoglycemic symptoms or any other adverse experiences will be reviewed and an attempt will be made to explain their occurrence. The subject's concurrent medications will be reviewed to ensure that dosages and compliance have not changed; any changes will be logged and subjects will be appropriately counseled. The entire study will last approximately 4 months.

Visit #	1	2	3
Week	0	8	16
Consent, inclusion / exclusion criteria	X		
Review of history / physical findings	X	X	X
CBC, Chemistry, FPG, HbA _{1c} , Urine pregnancy test ^a (obtained at MLK, SCFHC or CTRC)	X	X	X
Vitals, Weight, Height	X	X	X
Fasting insulin, calculation of HOMA-IR and QUICKI, hsCRP (obtained at CTRC, banked)	X	X	X
Randomization (if all criteria met)	X		
Dispense study medication supply	X	X	
Collect unused study medication supply; pill counts		X	X
Review of hypoglycemia	X	X	X
Review of adverse events		X	X
Reinforce nutrition / lifestyle	X	X	X
Review concurrent medications	X	X	X

^a For women of childbearing potential.

Assessment Measures (performed at CTRC):

- Vital signs, height and weight will be obtained at each visit, along with a brief review of the patient's history and physical findings at week 0 to look for exclusion criteria.
- Compliance with the subject's usual nutritional and lifestyle activities will be reviewed and reinforced.
- Changes in concurrent medications will be assessed at each encounter. Every effort will be made to avoid changes in concurrent medications that may influence carbohydrate or lipid metabolism (unless down-titration of SU is required).

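### As most naturally read, the 4-week laboratory waiver at Week 0 covers the urine pregnancy test, so a result up to 28 days old could support entry although current pregnancy is an exclusion

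*Combined protocol and SAP*

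**What the plan says.** All of this is in the combined protocol and SAP.

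- **Exclusion Criteria.** One bullet reads "Current pregnancy or lactation". The bullet before it excludes sexually active women of childbearing potential who do not use, or will not agree to use, reliable contraception.
- **Screening Visit (Week 0), test list.** One sentence gives the blood tests and then, after a semicolon, adds "urine will be collected for a urine pregnancy test (for women of childbearing potential".
- **Same section, MLK subjects.** "all blood and urine samples with the exception of fasting insulin and hsCRP will be drawn by the MLK outpatient phlebotomists", with results retrieved later.
- **Same section, waiver.** "The above laboratory tests with the exception of fasting insulin and hsCRP are not required if they have already been performed". The sentence sets a time limit and an access condition on the earlier test, which must have been done "by the laboratory within the previous 4 weeks and the results are accessible to the study team".
- **Same section, SCFHC subjects.** "any of the above laboratory test results performed within the previous 4 weeks will be requested by the investigators". Whatever was not done in that window is obtained at the CTRC.
- **Visit schedule table.** The row for CBC, chemistry, FPG and HbA1c also holds "Urine pregnancy test ^a (obtained at MLK, SCFHC or CTRC", marked at Weeks 0, 8 and 16. The row "Randomization (if all criteria met" is marked at Week 0 only. Study medication is dispensed at Weeks 0 and 8.

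**The concern.** A look-back of four weeks may be reasonable for a creatinine or a blood count. A pregnancy test is different: a negative result describes the day on which it was taken, whereas the exclusion concerns the woman's status at entry. If the waiver reaches the pregnancy test, a woman with an accessible recent result needs no test at Week 0, and the plan describes no other pregnancy test before the first supply of drug. What is at stake is participant safety, and whether the Week 0 testing rule supports the exclusion it is meant to serve.

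This is separate from the order of testing and randomization for women who are tested at Week 0. Settling that order would not help a woman for whom no Week 0 test is required.

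**Working it through.** The plan states no statistical figure to reproduce here. The check is a reading of the text followed by date arithmetic.

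**Step 1: does the waiver include the pregnancy test?** Two readings are possible.

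*Broad reading: every Week 0 test is waivable except fasting insulin and hsCRP.* In its favour:
- The waiver refers back to the tests above it, and the pregnancy test is the last item listed there.
- The exception is a closed list of two, and the pregnancy test is not on it.
- The MLK sentence, which stands between the list and the waiver, attaches the same two-item exception to blood and urine samples together. Urine is therefore in the set under discussion.
- The SCFHC sentence repeats the 4-week rule for any of the listed results, so both clinics are affected.
- The schedule table groups the pregnancy test with four items that are plainly waivable at Week 0.

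*Narrow reading: only the blood tests are waivable.* In its favour:
- The label for laboratory tests introduces the blood list, and urine comes in a separate clause after a semicolon.
- Both named exceptions are blood tests.
- The MLK sentence says who collects samples, not which tests are waived.

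The broad reading has more support, but the text does not exclude the narrow one.

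**Step 2: does another passage require a fresh test?** The Week 0 mark in the schedule does not settle this, because the same mark covers waivable tests. The Follow-Up Visits section requires pregnancy testing at follow-up but does not address Week 0. No section expressly requires a new test at Week 0 when a recent result exists.

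**Step 3: intervals under the broad reading.**

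| Input | Source | Value |
|---|---|---|
| Look-back window | Screening Visit (Week 0) | 4 weeks × 7 = 28 days |
| Randomization and first dispensing | Visit schedule table | Week 0 = day 0 |
| Next pregnancy test | Visit schedule table; Follow-Up Visits | Week 8 = 8 × 7 = 56 days |

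- Oldest result allowed at entry: 28 days.
- Longest scheduled gap between tests with the waiver: 28 + 56 = 84 days, of which up to 56 are on study drug.
- Scheduled gap with a test at Week 0: 56 days.
- Difference: 84 − 56 = 28 days, all of it before the first dose.

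These figures assume that the Week 8 visit is on time. The Study Medication section provides a 90-day supply partly to allow for variation in that visit, so an actual gap could be longer.

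**Step 4: how many women?** This cannot be computed. The documents give up to 60 subjects aged 18 to 75. They give neither the number of women of childbearing potential nor the share who would arrive with a recent clinic pregnancy test.

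**The case against.** The strongest reply is textual: the waiver may have been meant for blood tests only, in which case every woman of childbearing potential is tested at Week 0 and the gap disappears. This stands as a possible reading, and it rules out saying that the plan certainly waives the test. It does not remove the point, because staff at either clinic could reasonably follow the broader wording.

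The second reply is that the urine test is not the only safeguard. The contraception criterion excludes the women at greatest risk, and eligibility and history are reviewed at Week 0. That also stands, and it lowers the risk. A reader might otherwise infer that the plan has no means of applying the pregnancy exclusion, which goes too far. Still, contraception and history do not establish that a woman is not pregnant on the day, and the plan itself schedules pregnancy tests at every visit in addition to the contraception rule.

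The third reply is that the affected group may be very small or empty, since it needs a pregnancy test already done within 4 weeks with a result the team can see. That is fair, and nothing in the documents settles it.

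A reader might also infer that a woman found to be pregnant would leave the trial and cost it a Week 16 HbA1c. The documents do not support building on this. The Withdrawals section does not name pregnancy, although its list is open-ended. The Statistical Analyses section also plans last observation carried forward for missing data in the intent-to-treat analysis. No effect on the primary endpoint has been shown.

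**Conclusion.** The point holds as a safety and consistency matter. Read most naturally, the waiver lets a woman of childbearing potential from either clinic enter and receive study drug at Week 0 on a pregnancy test up to 28 days old, with up to 84 days between scheduled tests instead of 56. That sits badly with an exclusion for current pregnancy.

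The conclusion rests on three things: the broader reading of the waiver, a recent and accessible test result, and a Week 8 visit on schedule. The contraception criterion reduces the risk without removing it. The number of women affected is unknown and may be small. No claim is made about the HbA1c analysis, and none about what result should be in hand before drug is dispensed, which is for the sponsor to settle.

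**What to change.** - In the Screening Visit (Week 0) section, add the urine pregnancy test to fasting insulin and hsCRP as tests excepted from the 4-week waiver. Make the same change in the SCFHC sentence, so that the rule is the same for both clinics.
- In the visit schedule table, move the pregnancy test out of the row it shares with CBC, chemistry, FPG and HbA1c and give it a row of its own.
- Have the sponsor reconcile the Exclusion Criteria, the Screening Visit text and the schedule table, so that the Week 0 testing rule can support the pregnancy exclusion.

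The cost is a short wording change in two sentences, one table row, and one urine test for any woman who would otherwise have been waived. The test is already on the Week 0 schedule, so no new type of procedure is added.
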